17. APPENDICES76

1. OBJECTIVES

1.1 Study Design

This study was designed to enroll 50 subjects with untreated chronic lymphocytic leukemia/small lymphocytic lymphoma (CLL/SLL) who meet IWCLL 2008 criteria for initiation of therapy will initiate single-agent idelalisib (GS1101), a PI3K delta specific inhibitor, daily for the first two months on study, and begin ofatumumab at the start of the 3rd month following a complete response evaluation. The duration of combination therapy will be 8 months. All subjects will receive 8 weekly doses of ofatumumab, following which they will undergo another response evaluation. They will then continue with idelalisib during their 4 monthly doses of ofatumumab. The final primary endpoint response evaluation will occur two months after completion of ofatumumab, at 10 months following start of therapy. Therapy with idelalisib will continue throughout the ofatumumab therapy and after, until development of progressive disease. Once participants are receiving single agent idelalisib therapy they will be seen in clinic every 2 months. After treatment is complete subjects will be followed every 3-6 months at the treating investigator's discretion until initiation of a new therapy or death. Subjects who do not complete cycle 2 are not considered evaluable for the study efficacy objectives and may be replaced. Their data will be included in all toxicity evaluations.

As of 3/11/2016, Gilead has observed an excess of infectious deaths in three trials, one in upfront CLL, and as a result the FDA and Gilead are discontinuing enrollment to upfront CLL trials as well as discontinuing the administration of idelalisib to patients previously enrolled on these trials. All patients on this trial however may receive ofatumumab as planned and continue to be followed per protocol. Correlative analyses will continue as previously planned.

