5.4 Duration of Therapy

The planned duration of induction therapy is 8 months of induction therapy. For those still in the midst of induction, they may complete the planned 6 months of ofatumumab therapy followed by

CONFIDENTIAL

This document is confidential. Do not disclose or use except as authorized.

observation. Protocol follow-up may continue until achievement of CR, or indefinitely, until one of the following criteria applies:

- Disease progression,
- Intercurrent illness that prevents further administration of treatment,
- Unacceptable adverse event(s),
- Participant demonstrates an inability or unwillingness to comply with the oral medication regimen and/or documentation requirements
- Participant decides to withdraw from the study, or
- General or specific changes in the participant's condition render the participant unacceptable for further treatment in the opinion of the treating investigator.

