5.5 Duration of Follow Up

Once participants have completed study treatment they will be followed until initiation of new therapy following removal from study, or until death, whichever occurs first. They will be seen every 3 or 6 months in the follow up phase; this will be decided by their treating physician. Follow up will continue for up to 10 years. Participants removed from study for unacceptable adverse events will be followed until resolution or stabilization of the adverse event, and/or until initiation of new therapy for their disease, whichever is longer.

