5.6 Criteria for Removal from Study

Participants will be removed from study when any of the criteria listed in Section 5.4 applies. The reason for study removal and the date the participant was removed must be documented in the study-specific case report form (CRF). Alternative care options will be discussed with the participant.

In the event of unusual or life-threatening complications, participating investigators must immediately notify the Principal Investigator (or Protocol Chair) [name] at [contact] or pager at [contact] [name].

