 5. For ofatumumab, 2 lavender top tubes. Predose and end of infusion on cycle 3 day 1, cycle 3 day 8, cycle 3 day 15 and cycle 4 day 22 (end of weekly ofa), and cycles 5 and 8 day 1. Note: Predose only for cycle 3 days 8 and 15; and 2 and 6 mos post therapy, no end of infusion.
- For idelalisib, one lavender top predose and one lavender top 1.5 hours post-dose, on Cycles 1-3 Day 1, Cycle 4 Day 22, Cycle 8 Day 1 (last monthly dose of Ofatumumab) and 2 and 6 months after end of ofatumumab.
6. OSU: 3 ACD (yellow top) tubes, 8.5 cc each, + one sodium heparin (green top) tube at screen; 5 ACDs and one heparin on day 1 prior to therapy, 2 ACDs on cycle 1 day 15, 5 ACDs and one heparin on cycle 2 day 1, 3 ACDs and 1 sodium heparin (green top) tube at two month restage, and 2 ACDs on cycle 3 day 1.
 7. Mayo Clinic: 1 sodium heparinized (10 cc green top) tube. Bone marrow aspirate (a couple ccs) will be obtained at each timepoint. At screening only aspirate should be collected.
 8. SAEs and deaths for six months after completion of all therapy.
 9. Only in women of childbearing potential
 10. For those patients who are hepatitis B core antibody positive but surface antigen and HBV DNA negative, monitoring of HBV DNA or viral load is required during the on treatment period at least every 2 months and during follow-up at a minimum of every 2-3 months up to 12 months after the last dose. This testing is also required in the event of development of grade 1 or more elevation in LFTs.
 11. Subjects who discontinue therapy due to an adverse event, but have demonstrated a response of SD or better will enter the follow-up period and be followed every 3 or 6 months until documented relapse or PD, initiation of a new therapy, or for a total of 12 months of follow-up, whichever occurs first.
 12. Vitals Signs include: heart rate, respiratory rate, temperature, blood pressure and oxygen saturation.
 13. Chemistry: Electrolytes, BUN, creatinine, glucose, LDH, phosphate, uric acid, LFTs (total bilirubin, AST, ALT, alkaline phosphatase). Beginning C1D15 through C4D28 a comprehensive metabolic panel (electrolytes, BUN, creatinine, glucose, LDH, phosphate, uric acid, LFTs (total bilirubin, AST, ALT, alkaline phosphatase) will be obtained twice per week. If grade 1 or higher AST, ALT, or bilirubin elevations are noted please see Section 6.2 "Management of Hepatic AEs."
 14. Hematology: CBC, manual differential
 15. Weekly Ofatumumab proceeds through Cycle 4 Day 22.

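### Study calendar footnote 11 stops disease follow-up at 12 months for adverse-event discontinuers with SD or better, in conflict with Sections 5.5 and 1.1, so the secondary PFS can lose later progressions

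*Combined protocol and SAP*

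**What the plan says.** Table 10 in Section 9 attaches footnote 11 to the 3- or 6-monthly Long Term Follow-up column. The footnote reads: "Subjects who discontinue therapy due to an adverse event, but have demonstrated a response of SD or better will enter the follow-up period". They are then seen until relapse or PD, a new therapy, "or for a total of 12 months of follow-up, whichever occurs first". It does not say when the 12 months start.

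Section 5.5 says that patients removed for unacceptable adverse events are "followed until resolution or stabilization of the adverse event, and/or until initiation of new therapy for their disease, whichever is longer". It also sets a general limit: "Follow up will continue for up to 10 years". Section 1.1 follows subjects after treatment "until initiation of a new therapy or death".

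Section 10.1.7 defines PFS as study entry to objective progression or death. Section 14.2 estimates its median by Kaplan-Meier and gives no censoring rule. Table 10 has a separate yearly survival contact, by telephone or from a clinic note.

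**The concern.** PFS is a secondary objective, and it is also an outcome of the CT-scan objective as worded in both Section 1.3 and Section 14.2. A follow-up limit that depends on why treatment stopped removes progression information from a group selected by toxicity and by having at least stable disease.

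The loss is also lopsided: progression is no longer looked for, but a death can still be learned from the yearly contact. With no censoring rule, one analyst could censor such a patient when the limit is reached, and another could count a much later death as the PFS event although any earlier progression was never sought. Sites that follow the footnote and sites that follow Section 5.5 would collect different data on the same kind of patient.

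**Working it through.** **The rules applied to one patient.** Take a patient who stopped for an adverse event, had a PR, and 13 months later is untreated and without PD.

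| Source | Rule | At month 13 after stopping |
|---|---|---|
| Footnote 11 | first of PD, new therapy, 12 months | disease follow-up has ended |
| Section 5.5 | longer of event resolution and new therapy, within 10 years | continues |
| Section 1.1 | to new therapy or death | continues |

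One rule takes the earliest stopping point and another the latest. No passage gives either precedence.

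**Size.** The documents give no PFS assumption, event target or analysis date, so there is no figure to reproduce. They also give no adverse-event stop rate and no PFS for this regimen in untreated patients. The only input from the documents is 27 enrolled patients (Section 14.1). Everything else is assumed:

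- PFS is exponential with median 36 months, so L = ln 2 / 36 = 0.01925 per month.
- A fraction f = 0.15, 0.30 or 0.50 stops for an adverse event at a time u, uniform on months 1 to 8.
- The limit falls at u + 12.

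*Hidden events by month H, equal hazards.* Hidden = 27 × f × (E[exp(−L(u+12))] − exp(−L·H)).

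The expectation is (exp(−13L) − exp(−20L)) / (7L) = (0.7786 − 0.6804) / 0.1348 = 0.728.

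At H = 36, exp(−L·H) = 0.5, so hidden = 27 × f × 0.228.

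| H (months) | All events, 27 × (1 − exp(−L·H)) | f = 0.15 | f = 0.30 | f = 0.50 |
|---|---|---|---|---|
| 36 | 13.5 | 0.9 | 1.8 | 3.1 |
| 60 | 18.5 | 1.7 | 3.3 | 5.6 |
| 120 | 24.3 | 2.5 | 5.1 | 8.5 |

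Under these assumptions the counts are upper bounds. They treat deaths as hidden although the yearly contact may catch them, and they ignore patients who leave disease follow-up for new therapy under any of the rules. If only 70% of adverse-event stoppers have SD or better, the 36-month row falls to 0.6, 1.3 and 2.2.

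*Shift in the Kaplan-Meier median.* Patients are censored at the limit. Large-sample simulation (1,000,000 patients), others' median 36 months:

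| f | Stoppers' median (months) | True overall median | Kaplan-Meier median | Shift |
|---|---|---|---|---|
| 0.15 | 12 | 30.3 | 32.2 | +1.9 |
| 0.30 | 12 | 25.3 | 28.0 | +2.7 |
| 0.50 | 18 | 25.0 | 28.1 | +3.1 |
| 0.15, 0.30, 0.50 | 36 | 36 | 36 | 0 |
| 0.30 | 48 | 39.1 | 37.3 | −1.8 |
| 0.50 | 48 | 41.4 | 38.2 | −3.2 |

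*Sampling SD of the median, n = 27, equal hazards (20,000 replicates).* With 60 months of follow-up it is 9.2 months without the limit, 9.7 with the limit at f = 0.30 and 10.3 at f = 0.50. With 120 months it is 10.1, 11.7 and 13.5. The loss of precision is therefore visible but not large.

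**The case against.** The strongest reply is that the effect is small. PFS is a descriptive, single-arm secondary estimate in 27 patients with no test attached. Kaplan-Meier treats the limit as censoring, the median does not move at equal hazards, and the assumed shifts lie well inside the sampling SD. All of that stands. It limits the size of the point but does not remove the contradiction, and progression dates that were never sought may not be recoverable later.

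Two stronger readings are tempting, and the documents do not support them.

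- A reader might infer that follow-up ends at the adverse event itself, or at CR. Section 5.4 says "Protocol follow-up may continue until achievement of CR, or indefinitely, until one of the following criteria applies" and lists unacceptable adverse events, and Section 5.6 adds: "Participants will be removed from study when any of the criteria listed in Section 5.4 applies". But Section 5.4 is headed as duration of therapy, several of its items concern further treatment or oral dosing, and Section 5.5 says how patients are followed after removal. The inference needs 5.4 to be read without 5.5. What remains is loose wording.
- A reader might infer that the idelalisib stop of 3/11/16 puts every patient under the 12-month limit. Sections 1.1 and 2.5 describe a programme-wide stop prompted by deaths in other trials, not individual stopping for an adverse event. Section 2.5 gives those patients their own rule: followed per protocol to further therapy, then for survival.

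**Conclusion.** The conflict between footnote 11 and Sections 5.5 and 1.1 is real and unreconciled. If sites apply the footnote, the secondary PFS loses progressions and precision in adverse-event discontinuers with SD or better. Bias should not be taken as given: it arises only if their later progression hazard differs from that of the other patients, and the documents do not say whether it does.

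The size is modest: about 1 to 3 of 13.5 expected events at 36 months as an upper bound, and a median shift between none and about 3 months in either direction. These figures rest on assumed stop rates, exponential PFS and a 36-month median, none of which comes from the documents. The primary ORR analysis is unaffected. The passages should still be reconciled, because the remedy is cheap and follow-up continues although enrollment is closed.

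**What to change.** - **Footnote 11:** remove the 12-month limit on progression follow-up. Disease follow-up then runs to PD, new therapy or death, within the 10-year limit of Section 5.5 and whatever the reason treatment stopped, followed by the yearly survival contact. State the same rule in 5.5 and 1.1.
- **Section 14.2:** state that stopping treatment is not a PFS censoring event and that patients alive without PD are censored at their last disease assessment. State also how patients who start new therapy before PD are handled. One option is to censor them at the last disease assessment before the new therapy, so that a later death is not counted after progression follow-up has ended.
- **Reporting:** give the number of patients whose disease follow-up ended under footnote 11.
- **Editorial only:** clarify that the Section 5.4 criteria end treatment, not the follow-up described in 5.5.

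The cost is an amendment with IRB approval (Section 13.1), plus 3- or 6-monthly visits beyond 12 months for a few patients, which 5.5 already provides for. The study opened in June 2014 (Section 2.5), so some early discontinuers may already have passed 12 months by the March 2016 amendment. Recovering their progression status could require re-contact or record review.

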10. MEASUREMENT OF EFFECT

10.1 Antitumor Effect – CLL

Definition of response, relapse, and refractory disease

Assessment of response should include a careful physical examination and evaluation of the blood and marrow. CT scanning will be performed as indicated in the table of assessments (required at screening, and at key response assessments).

It is important to note that idelalisib may result in increasing lymphocytosis at the start of the study, which will not be considered evidence of progressive disease. In fact, an isolated increase in lymphocytosis, in the absence of other signs of disease progression including worsening lymphadenopathy, neutropenia, anemia or thrombocytopenia or disease symptoms, will not in this study be sufficient to define progressive disease. This modification to the standard criteria is needed because idelalisib can cause redistribution of CLL lymphocytes from sanctuary sites into peripheral blood, in the absence of progressive disease.

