some subjects or could be seen repeatedly in subjects who had interruption and resumption of drug therapy (eg, due to intercurrent illness). The characteristics of this lymphocytosis indicated a mobilization of CLL cells from tissues rather than a proliferative event or a disease flair. The effect was evident within 4 hours of initiating treatment, was asymptomatic, and was associated with quiescence of CLL cells as indicated by reductions in AKT phosphorylation and decreases in circulating levels of disease-associated chemokines, CCL3 and CCL4, and the stroma-derived chemokine, CXCL13. The lymphocyte mobilization phenomenon is consistent with in vitro data showing that idelalisib depresses chemokine-mediated signaling between CLL cells and stromal cells [10]. These preclinical data support the concept that drug-mediated PI3K δ inhibition releases CLL cells from sanctuary sites in lymph nodes and bone marrow. This action is not unique to idelalisib alone. Drugs that inhibit spleen tyrosine kinase (SYK) [11], Bruton tyrosine kinase (BTK) [12], or mTOR [13] cause a CLL cell redistribution from tissue sites to the peripheral blood. Because of the occurrence of this type of pattern, investigators working with idelalisib or inhibitors of these other pathways now rely upon measures of disease control other than peripheral blood lymphocyte count in determining whether a patient's disease has progressed.

An analysis of steady-state idelalisib plasma concentrations (Day 28 C_{max} , AUC_{0-6h} , or C_{trough}) relative to dose in subjects with both NHL and CLL showed increases in these parameters through the dose level of 150 mg/dose BID. At higher doses, flattening of the mean dose-plasma exposure curve was observed, resulting in smaller incremental increases in exposure. Considering all safety, efficacy, and pharmacokinetic findings together, the data supported 150 mg/dose BID as an appropriate idelalisib monotherapy starting dose for future studies in patients with CLL and other lymphoid malignancies.

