This study activated for enrollment on June 16, 2014, and since then 15 patients have initiated on therapy. Among the first 8 patients to reach cycle 2, two patients developed grade 4 transaminitis. Transaminitis is a well-known side effect of idelalisib, and included as a black box warning in the FDA approved label. In these two cases the onset was rapid, and continued to increase after discontinuation of the drug. We have therefore previously amended the protocol to significantly increase the frequency of LFT monitoring during the high risk period. Additional observation has shown that this transaminitis appears to be inflammatory, based on the results of two liver biopsies showing a CD8 T cell infiltrate and the response of these patients to steroids and/or mycophenolate mofetil. We have developed an algorithm for the early initiation of steroids with the first signs of transaminitis which together with the frequent monitoring has resulted in predictable safety and much shorter drug interruptions. This amendment served to further refine that treatment algorithm.

An amendment was submitted in January 2015 to add correlative studies, in particular sequencing analysis of the clonal composition of CLL in PB vs BM at baseline, mid treatment and at final restaging. This analysis will still occur.

Rationale for Current Amendment 3/14/16

This amendment will take all patients off idelalisib, but allow them to receive ofatumumab and be followed per protocol assessments. All patients had discontinued idelalisib as of 3/11/16. They will undergo a full disease restaging with correlative samples within 30 days and be followed per protocol until further therapy, and after that just for overall survival.

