10.1.3 Progressive disease

Progressive disease during or after therapy is characterized by at least one of the following:

- **Lymphadenopathy.** Progression of lymphadenopathy is often discovered by physical examination and should be recorded. In CLL, the use of CT scans usually does not add much information for the detection of progression or relapse. Therefore, the use of imaging methods to follow CLL progression is at the discretion of the treating physician.
- Disease progression occurs if one of the following events is observed: **(1)** Appearance of any new lesion, such as enlarged lymph nodes (>1.5 cm), splenomegaly, hepatomegaly, or other organ infiltrates. **(2)** An increase by 50% or more in greatest determined diameter of any previous site. **(3)** An increase in the previously noted enlargement of the liver or spleen by 50% or more or the de novo appearance of hepatomegaly or splenomegaly.

CONFIDENTIAL

This document is confidential. Do not disclose or use except as authorized.

- **Transformation to a more aggressive histology (eg, Richter syndrome). Whenever possible, this diagnosis should be established by lymph node biopsy.**
- **Occurrence of cytopenia (neutropenia, anemia, or thrombocytopenia) attributable to CLL.**

During therapy. Cytopenias may occur as a side effect of many therapies and should be assessed according to Appendix C.

After treatment. The progression of any cytopenia (unrelated to autoimmune cytopenia), as documented by a decrease of Hb levels by more than 20 g/L (2 g/dL) or to less than 100 g/L (10 g/dL), or by a decrease of platelet counts by more than 50% or to less than $100 \times 10^9/L$ (100 000/ μ L), which occurs at least 3 months after treatment, defines disease progression, if the marrow biopsy demonstrates an infiltrate of clonal CLL cells and there is no evidence for an autoimmune process.

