10.1.7 Time to progression, progression-free survival, and overall survival

Time to progression (TTP) is defined as the time from study entry until objective disease progression (see above). Progression-free survival (PFS) is defined as the time from study entry until objective disease progression or death. Overall survival is defined as the time from study entry until death from any cause, and is measured in the intent-to-treat population.

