10.1.8 Relapse

Relapse is defined as a patient who has previously achieved the above criteria of a CR or PR or nodal response with lymphocytosis, but after a period of 6 or more months, demonstrates evidence of disease progression as described above.

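### Isolated lymphocytosis stays exempt from progressive disease after idelalisib, its only stated reason, was withdrawn, so off-drug blood-only progression enters PFS late or not at all

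*Combined protocol and SAP*

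**What the plan says.** Section 10.1 first notes that idelalisib may raise the lymphocyte count early in the study. It then sets a general rule: a rise without other signs of progression (worsening nodes, cytopenias, disease symptoms) "will not in this study be sufficient to define progressive disease". The reason follows: "This modification to the standard criteria is needed because idelalisib can cause redistribution of CLL lymphocytes from sanctuary sites into peripheral blood". The rule has no end date and no on-drug condition.

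Section 10.1.3 opens: "Progressive disease during or after therapy is characterized by at least one of the following". Its list covers nodes and organs, transformation, and cytopenia attributable to CLL. It has no lymphocyte-count criterion.

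The time-to-event definitions rest on that list. PFS (10.1.7) "is defined as the time from study entry until objective disease progression or death", and relapse (10.1.8) applies to a previous responder who, after at least 6 months, "demonstrates evidence of disease progression as described above". Section 14.2 estimates median PFS by Kaplan-Meier and names no alternative scoring.

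The March 2016 amendment rationale in section 2.5 states: "All patients had discontinued idelalisib as of 3/11/16". After restaging, patients are to "be followed per protocol until further therapy, and after that just for overall survival".

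**The concern.** Under the design in section 1.1, idelalisib continued until progression. For a patient treated as planned, first progression would be judged on drug, and a study-wide exemption fitted its reason. The amendment moved everyone to off-drug follow-up but left section 10.1 unchanged. The reason ended while the scope of the rule did not.

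At stake is PFS, a named secondary endpoint, together with TTP and relapse. A patient whose disease returns in the blood alone, off drug, is counted as progression-free until something else happens. Such a patient could also be re-treated first: section 3.1.3 accepts progressive lymphocytosis as sufficient by itself to indicate treatment at entry. After new therapy the protocol follows survival only, and section 14.2 is silent on whether the patient is censored, counted as an event at that point, or counted only at death.

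**Working it through.** **Text check**

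1. Section 10.1 exempts isolated lymphocytosis throughout the study, and its only reason is idelalisib.
2. Section 10.1.3 applies during and after therapy and has no lymphocyte criterion, so nothing restores one off drug.
3. Sections 2.5, 5 and 5.2.1 put all patients off idelalisib from 3/11/16.
4. PFS, TTP and relapse all use the same progression definition. From 1 to 3, off-drug blood-only progression is not an event until a listed sign or, for PFS, death.
5. The other signs are narrow. Follow-up CT is discretionary (Study Calendar, footnote 2). Post-treatment cytopenia counts only from 3 months after treatment and needs marrow confirmation (10.1.3). Symptoms lift the exemption in 10.1 but are not a criterion in 10.1.3.

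**Is the rise tied to drug exposure?** Section 2.2.2 reports that it "could be seen repeatedly in subjects who had interruption and resumption of drug therapy", which points that way. Section 2.2.1 gives a half-life of 6 to 10 hours in healthy subjects, so five half-lives are 30 to 50 hours. That covers the parent drug only. Section 2.1 says that metabolite levels exceed the parent's in humans, and no metabolite half-life is given. Nothing states how long mobilised cells stay in blood after stopping.

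**Size.** The plan gives no PFS assumption and no share of blood-only progressions, so there is no plan figure to reproduce. What follows is illustration only, and M, d, q and D are all assumptions.

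- M: median PFS in months if blood-only progression counted; constant hazard, S(t) = 2^(−t/M)
- d: months on idelalisib, at most 20.8 (activation 6/16/14 to 3/11/16)
- q: share of off-drug first progressions that are blood-only
- D: months until another sign appears

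Scored D months late: solve S(t) + q[S(max(d, t−D)) − S(t)] = 0.5. When t−D > d this gives t = M[1 + log2(1 − q + q·2^(D/M))]. If the patient is instead censored at new therapy (a rule the plan does not state), the median is d + (M−d)/(1−q) for d < M.

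With M=24, d=12, q=20%:

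- D=6: 24[1 + log2(0.8 + 0.2×1.189)] = 25.3
- D=12: 24[1 + log2(0.8 + 0.2×1.414)] = 26.8
- Censored: 12 + 12/0.8 = 27.0

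| q | 6 months late | 12 months late | censored |
|---|---|---|---|
| 10% | 24.6 | 25.4 | 25.3 |
| 20% | 25.3 | 26.8 | 27.0 |
| 30% | 25.9 | 28.1 | 29.1 |

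At q=20%, taking d=6 and d=20.8, the three branches span 14.0 to 16.6 for M=14, 24.8 to 28.5 for M=24 and 37.3 to 43.5 for M=36.

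Patients reclassified by month H, without censoring: 27·q·[S(12) − S(H)]. At q=20%: H=36 gives 5.4×(0.707−0.354) = 1.9, and H=60 gives 5.4×(0.707−0.177) = 2.9. Over q=10% to 30% the range is 1.0 to 4.3.

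These formulas apply q to every off-drug PFS event, deaths included, although q is defined for progressions. The results are therefore upper illustrations for the stated q.

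**Against sampling error.** With n=27 and no censoring, a true 24-month median is estimated between about 13 and 40 months (2.5th to 97.5th percentile). The largest shift in the table, 29.1 − 24 = 5.1 months, is well inside that range.

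**Direction at n=27.** Simulation with M=24, d=12, q=20% and censoring uniform over 12 to 60 months gave:

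| scoring | median rose | unchanged | fell |
|---|---|---|---|
| 6 months late | 42% | 54% | 4% |
| 12 months late | 53% | 45% | 3% |
| censored | 53% | 47% | 0% |

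Rows may not sum to 100 because of rounding.

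**The case against.** The study-wide wording may be deliberate. Section 2.2.2 says that investigators using these inhibitors judge progression by measures other than the lymphocyte count, and one definition throughout avoids changing criteria partway along a curve. This stands as a reason to keep the existing PFS as the protocol analysis. It does not answer the point, because that statement concerns working with the drugs and not patients taken off them.

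The obvious remedy is to rewrite 10.1 and 10.1.3, and the objection to that also stands. Progression is a listed criterion in section 5.4 and leads to removal from study under 5.6, while patients may still be completing ofatumumab. A new progression definition would change a stopping trigger and redefine TTP and relapse after the fact. The remedy must therefore be confined to scoring.

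A reader might infer that events are always lost once new therapy starts. The documents do not say so: survival follow-up still captures death, which is a PFS event, and no censoring rule is stated. For the same reason the working includes no branch in which an affected patient is never scored.

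Finally, the documents supply neither the lymphocyte criterion nor a duration for redistribution after stopping, and section 2.5 describes ofatumumab as clearing blood disease very effectively, so q could be small. All of this stands. It limits what can be claimed about size and obliges the sponsor to write down and justify the missing rules.

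**Conclusion.** The concern holds as a gap between a rule and its stated reason. After 3/11/16, off-drug blood-only progression is scored late or possibly not at all in PFS, TTP and relapse. Duration of response (10.2) is affected only if recurrence there is read through 10.1.3. The primary ORR is unaffected.

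For each affected patient the event can only move later or be lost. A reader might go further and infer that the reported median PFS must be too long. That does not follow at n=27: the Kaplan-Meier median is often unchanged and can fall. For example, an event at 10 months with censoring at 12, 14 and 16 gives a median not reached; moving the event to 20 gives a median of 20.

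The size is not determinable from the documents, may be zero, and is likely within sampling error. The illustrative figures rest on assumed M, d, q, D and constant hazard, and overstate the effect for a given q. This merits an inexpensive improvement to a secondary analysis and does not undermine the trial's main result.

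**What to change.** Leave the definition in 10.1 and 10.1.3 as it is, for patient management and for the protocol PFS analysis. Add to section 14.2 one Kaplan-Meier PFS, labelled supplementary. For scoring only, it would also count lymphocyte progression under the standard criteria that 10.1 says it modifies, when this occurs off idelalisib and after a window. Before any re-scoring, write down:

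- the lymphocyte criterion, which the documents do not reproduce, and its reference count;
- the window after the last idelalisib dose and its basis;
- whether new CLL therapy before progression is censored, an event, or followed to death.

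Report the number of patients reclassified; zero would itself be informative.

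The cost is a short addition to the plan and one re-scoring of blood counts with differential already scheduled in long-term follow-up (Table 10, footnote 14). The downsides are that PFS may look shorter, the rule is post hoc, event dates are known only to the 3- or 6-month visit, and a differential count does not prove that a rise is clonal (Table 10 lists no flow cytometry in long-term follow-up).

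Separately, reconcile Study Calendar footnote 11 with section 5.5 for patients who stop because of an adverse event. The footnote ends follow-up at 12 months at the latest. Section 5.5 follows them to resolution or stabilisation of the event and/or new therapy, whichever is longer, within follow-up of up to 10 years. The choice determines how long PFS is observed.
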